Recruitment, Study Participants, and Procedures- Our target sample size is up to 150 Hispanic smokers. We will coordinate with the safety managers of the participating construction sites to identify smokers who are interested in quitting smoking and arrange a visit to meet these workers. On day 1, two bilingual PH graduate assistants will approach these workers during their break to explain the study, complete the screening, and then obtain the consent form from those who are eligible. To participate in the study participant should be Hispanic male construction workers on site who are \geq 18 year old and have smoked \geq 5 cigarettes/day in the past year. Additionally, potential participants need to be available on site in the following two days, have access to telephone, have no plans to move in the next six months, and be interested in making a serious quit attempt in the next 30 days, and have no contraindication to NRT. Exhaled carbon monoxide levels and saliva cotinine will be tested among eligible participants to verify the self-reported smoking status. Individuals who decline to participate or who are ineligible (e.g., non-Hispanics, women) will be referred to the QL and provided with brochures that include information about the QL contact number and services. They will also be given a flyer about the UM Quitville smoking cessation study for which they may be eligible (only for English speakers). Those who are potentially eligible and interested in participating in the study will sign a consent form, then undergo a baseline screening to confirm eligibility and to collect information about: demographics, job characteristics, acculturation,⁴¹ smoking history, nicotine dependence,⁴² stages of change,⁴³ quit ladder,⁴⁴ smoking self-efficacy,⁴⁵ depression,⁴⁶ social support,⁴⁷ exposure to secondhand smoke, and quality of life. All questionnaires, informed consent, and educational materials will be available in English and Spanish and will be administrated by the bilingual graduate assistants. After completing the baseline assessment, a second visit in the following day will be scheduled to provide the intervention. If time does not permit to complete the entire baseline assessment, the exhaled carbon monoxide and saliva cotinine test, demographics and smoking behavior questions will be administered on-site and the remainder will be given to the

STUDY PROTOCOL AND ANALYSIS PLAN

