Outcome Measures- This pilot study aims to explore the acceptability potential and efficacy of the developed intervention compared to QL. *Main outcomes* include: 1) estimating yield (number of workers available divided by number eligible; and number eligible divided by number randomized), 2) facilitators and barriers to delivering the intervention in the proposed setting, 3) willingness of participants to be randomized and acceptability of the intervention, 4) follow-up rates and response rates to questionnaires, adherence/compliance rates, and the time needed to collect and analyze data, and 5) exploring the “willingness” of the target population to be involved in the research design and conduct.⁶⁰⁻⁶² *Potential efficacy outcomes* will focus on comparing prolonged abstinence (defined as no smoking, not even a puff, after a grace period of two weeks after quit date), and point-prevalent abstinence (defined as self-report of not smoking in the past 7-days; not even a puff) confirmed

STUDY PROTOCOL AND ANALYSIS PLAN

by saliva cotinine level of <15ng/ml at 6-month between the two study arms. For individuals who do not quit entirely, the decrease in smoking (i.e., cigarettes/day) will be assessed.^{63,64} Relapse is defined as smoking at least once/week on two consecutive weeks.⁶⁵ Secondary outcome measures will focus on differences in stage of change/readiness to quit,⁶⁶ and treatment adherence according to intervention assignment.³⁷

All participant data will be coded with an identification number and only approved personnel will have access to the key linking identification numbers with participant names. Data will be stored and managed in REDCap and accessed only by approved study personnel. Paper interview instruments will be stored in a locked filing cabinet.

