Although these adverse events have been reported in those who use NRT, they have been infrequent and are less likely to be observed in persons who are regular cigarette smokers. In addition, many of these same symptoms are reported by persons who quit smoking without NRT, and have been attributed to nicotine withdrawal from smoking cessation.

9) Potential Benefits to Subjects*

Participants will benefit by being involved in a no-cost program that may help them to quit smoking, reducing their risk for a variety of health conditions. Given the substantial potential benefits and the minimal risks for participants involved in this project, it is felt that the benefits significantly outweigh the possible risks.

10) Recruitment Methods

Two bilingual (English, Spanish) public health graduate students will approach construction workers either at their morning or noon food break at multiple construction sites in South Florida in partnership with the lunch truck service. Using a verbal consent script, potential participants will be asked if they are interested in participating in our study. If they agree, they will be asked a series of questions to determine whether they are eligible (Hispanic male construction workers who are \geq 18 years old and have smoked \geq 5 cigarettes/day in the past year). Additionally, potential participants need to have access to telephone, have no plans to move in the next six months, and be interested in making a serious quit attempt in the next 30 days. Individuals who decline to participate will still be encouraged to quit smoking, and given a list of available cessation resources. Those willing to participate but who are ineligible (e.g., non-Hispanics, women) will be referred to the QL and provided with brochures that include information about the QL contact number and services. Those who are potentially eligible and interested in participating in the study will be consented, then undergo a baseline screening to confirm eligibility and to collect information. All questionnaires, informed consent, and educational materials will be available in English and Spanish and will be administrated by the bilingual graduate assistants.

11) Local Number of Subjects

We seek to enroll up to 150 participants who are eligible according to the inclusion criteria.

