To avoid intervention contamination within participating construction worksites, the RCT design will be a two-group cluster randomized design with seven sites per group. Our resources for this R21 allow seven subjects per group. We assume that the intra-cluster correlation will be low (0.01). We will use a two-group comparison of proportions at the two-tailed alpha level. Assuming that 10%-15% of the control group and 25% of the intervention group respond to the intervention, we will have 23% power to detect a 10% difference and 50% power to detect a 15% difference. To achieve 80% power

STUDY PROTOCOL AND ANALYSIS PLAN

for a 10% and 15% difference under the same assumptions would require sample sizes of 64 and 16 subjects per site, respectively.

12) Confidentiality

Participant names will be replaced with ID numbers and a key linking the two will be kept separate from other data and accessed only by Drs. [name] and [name]. Survey data will be stored on Dropbox and accessible only by approved study personnel. Survey data from the RCT will be stored and managed in REDCap. These data will be stored for the duration of the study protocol and until all data analysis is complete and manuscripts have been published.

13) Provisions to Protect the Privacy Interests of Subjects

Participants will interact with only a limited number of approved study personnel and will be assured that their personal information will be kept private, will be used only for research purposes, and will not be accessible to non-study personnel.

14) Consent Process

Verbal consent will first be obtained after potential participants are screened on site. Those who verbally consent will then sign a written consent before the intervention begins. Because we are recruiting Hispanic participants the consent documents will be available in both English and Spanish.

STUDY PROTOCOL AND ANALYSIS PLAN

References

1. [name] DJ, Fleming LE, Arheart KL, et al. Smoking rate trends in U.S. occupational groups: the 1987 to 2004 National Health Interview Survey. *J Occup Environ Med.* Jan 2007;49(1):75-81.
2. [name] DJ, Fleming LE, McCollister KE, et al. Healthcare provider smoking cessation advice among US worker groups. *Tob Control.* Oct 2007;16(5):325-328.

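### Sections 10 and 14 put interest and screening in opposite orders; under Section 10's order, first-ask refusers leave the eligible count and refusal is misread as ineligibility in the yield outcome

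*Combined protocol and SAP*

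**What the plan says.** Section 10 (Recruitment Methods) opens the contact with the question of interest: "Using a verbal consent script, potential participants will be asked if they are interested in participating in our study". Eligibility comes second and is conditional: "If they agree, they will be asked a series of questions to determine whether they are eligible". The section then treats decliners and willing-but-ineligible workers as separate groups, which fits eligibility being learned only among the willing. A further decision follows: "Those who are potentially eligible and interested in participating in the study will be consented, then undergo a baseline screening to confirm eligibility".

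Section 14 (Consent Process) gives the other order: "Verbal consent will first be obtained after potential participants are screened on site".

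Section 5 (Recruitment, Study Participants, and Procedures) is mixed. Staff are to "approach these workers during their break to explain the study, complete the screening, and then obtain the consent form from those who are eligible". Later in the same paragraph the form is signed before the baseline screening that confirms eligibility. The paragraph does not say whether interest in the study is asked before or after the first screening questions.

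The outcome affected is yield, the first main outcome in the opening summary and in Section 7 (Outcome Measures): "number of workers available divided by number eligible; and number eligible divided by number randomized". Willingness to be randomized is also a main outcome, with no denominator given. No section says how workers who decline before screening are logged, and the Data Analysis text does not address yield.

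**The concern.** Staff cannot follow Sections 10 and 14 together at first contact, and the two orders produce different eligible counts from the same workers. Under Section 10 a worker who says no at the first question is never asked about age, smoking or the other criteria. If he was in fact eligible, he is missing from the eligible count but still present among those available. His loss then appears in the available-to-eligible step, as though he were ineligible, and not in the eligible-to-randomized step, where refusal belongs.

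The two-step yield exists to separate these two kinds of loss, and the protocol intends the pilot to inform a larger study. A planner needs to know whether workers are lost because few qualify or because those who qualify decline, since the remedies differ.

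**Working it through.** The documents give no expected yield, uptake or refusal rate, so there is no planned figure to reproduce. The check compares the two orders algebraically and then with assumed inputs.

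**Definitions.** N is workers available and e the share eligible. Let a be the share of eligible workers who agree at the first ask, and c the share of screened-eligible workers who then consent. Enrolled workers are treated as randomized. The order of asking is assumed not to change who finally joins, so under either order R = N × e × a × c.

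**Section 10 order.** Only first-ask agreers are screened.
- Observed eligible = N × e × a
- Uptake (randomized/eligible) = c, so eligible/randomized = 1/c
- Available/eligible = 1/(e × a)

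**Screening before interest.** All are screened.
- Observed eligible = N × e
- Uptake = a × c, so eligible/randomized = 1/(a × c)
- Available/eligible = 1/e

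Section 10's order therefore multiplies both uptake and available/eligible by 1/a. The product of the two yield ratios, available/randomized, is 1/(e × a × c) either way.

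**Range, with a and c assumed.** Each cell shows uptake, then eligible/randomized in brackets.

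| a | c | Section 10 order | Screening first |
|---|---|---|---|
| 0.3 | 1.0 | 1.00 (1.00) | 0.30 (3.33) |
| 0.5 | 1.0 | 1.00 (1.00) | 0.50 (2.00) |
| 0.9 | 1.0 | 1.00 (1.00) | 0.90 (1.11) |
| 0.3 | 0.8 | 0.80 (1.25) | 0.24 (4.17) |
| 0.5 | 0.8 | 0.80 (1.25) | 0.40 (2.50) |
| 0.9 | 0.8 | 0.80 (1.25) | 0.72 (1.39) |
| 0.5 | 0.6 | 0.60 (1.67) | 0.30 (3.33) |

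**In counts, with assumed N = 300, e = 0.40, a = 0.5, c = 0.8.**
- Screening first: 300 × 0.40 = 120 eligible; 120 × 0.5 × 0.8 = 48 randomized. Available/eligible = 300/120 = 2.5; eligible/randomized = 120/48 = 2.5; product 6.25.
- Section 10: 120 × 0.5 = 60 observed eligible; 60 × 0.8 = 48 randomized. Available/eligible = 300/60 = 5.0; eligible/randomized = 60/48 = 1.25; product 6.25.

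The same 48 men join from the same 300. The 60 eligible first-ask refusers have moved from the refusal step to the ineligibility step.

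**The case against.** The strongest reply is that overall throughput is unharmed. Available/randomized is the same under both orders, so a planner who uses both ratios together will not be misled about how many workers must be approached. This stands, and it limits the point to the split between the two steps.

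The number of hidden eligible refusers may also be small. Interest in a serious quit attempt within 30 days is itself an inclusion criterion, so some who turn down the study would have been ineligible on that ground. Section 5 also has safety managers identify smokers who want to quit before the visit. Both could bring a close to 1, where the bias is slight (a = 0.9, c = 1: 1.00 against 0.90). This is plausible, but nothing in the documents settles it, and under Section 10 the pilot could not show it.

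A reader might infer more than the text supports:
- *Eligible refusers are never counted, so uptake is near 100% by construction.* Section 10 keeps a second decision after the eligibility questions, and eligible workers who decline there can be counted. Uptake is near 100% only if c is near 1, which the documents do not say.
- *A full trial would expect double the enrolment.* This would require dropping the available/eligible ratio and taking the eligible count from elsewhere.
- *Section 5 is a clear screen-first text.* It is not. The direct conflict is between Sections 10 and 14.
- *Sites may differ in order and so cannot be pooled.* The protocol describes two graduate assistants and common training, and nothing suggests that the order varies by site.
- *Section 14 contradicts Section 5 on written consent.* Section 14 requires it before the intervention and Section 5 before baseline. Section 5's timing satisfies both.

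**Conclusion.** The point holds in limited form. Sections 10 and 14 conflict on whether interest is asked before or after screening, and Section 5 does not resolve it. Under Section 10's order, observed uptake is inflated by a factor 1/a, as is available/eligible, while eligible/randomized is pulled toward 1. The direction follows from the procedure. The size depends on a, which the documents do not give; over the assumed range 0.3 to 0.9 with c = 1, the comparison is 1.00 against 0.30 to 0.90. This rests on treating enrolled workers as randomized and on the order of asking not changing who joins.

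The consequence is confined to the yield outcome and to any willingness figure that uses the eligible count as its denominator: refusal is recorded as ineligibility. It is worth correcting because yield is the first main outcome and the correction is cheap.

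**What to change.** State one order in Sections 5, 10 and 14:

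1. The verbal script asks only for permission to be screened.
2. The short eligibility questions go to every worker who permits this.
3. Interest in joining is then asked of, and recorded for, every eligible worker.

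Log by site the numbers available, declining screening, screened, eligible and consented. Report uptake as consented/eligible, and show unscreened decliners separately with a range for their unknown eligibility. If D workers decline screening, E are found eligible and R consent, uptake lies between R/(E + D), with all decliners eligible, and R/E, with none eligible.

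The cost is wording in the protocol and script, plus about a minute of screening for workers who later decline. The change reduces the problem without removing it: those who refuse screening still have unknown eligibility. The gain depends on workers permitting a short screen more readily than they agree to join a study.

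The Data Analysis text is in the past tense and refers to 17 participating sites, so recruitment may be over. In that case, state which order was used. If it was Section 10's, report uptake as conditional on first-ask interest, with the number of unscreened decliners if it was kept.
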